6.4 Non-Medication Therapies and Surgery Details

Prior and concomitant non-medication therapies will be presented in a by-subject listing for each treatment group. All surgical information will appear in data listings.

Statistical Analysis Plan Version: 2.0

Effective Date: 08OCT2018

7.0 Measurements of Treatment Exposure and Compliance

Because the single dose of study medication is administered at the study center by trained study personnel, compliance with study medication is not expected to be an issue. A listing of all study medication exposure (including information on any partial administrations) will be provided.

8.0 Efficacy Evaluation

8.1 Overview of Analysis Issues

8.1.1 Handling of Dropouts or Missing/Invalid Data

Subjects with missing or invalid PI NPRS data will be imputed using the following rules.

Subjects who require rescue medication will record their pain intensity (PI) NPRS, Pain Relief (PR) and Patient Rating of Treatment Satisfactoriness scores within 5 minutes prior to first use of rescue medication. These are referred to as 'pre-rescue' PI, PR, and Patient Rating of Treatment Satisfactoriness scores, respectively. Any scheduled PI or PR assessments scheduled within 4 hours after administration of rescue medication will be replaced by the pre-rescue score in the efficacy analysis. This method of replacement is referred to as the windowed Last Observation Carried Forward (wLOCF).

After any scheduled PI/PR scores within 4 hours after rescue are appropriately replaced by the pre-rescue PI/PR scores, any other scheduled PI/PR scores that are still missing intermittently and are not within 4 hours after rescue medication will be imputed using linear interpolation between adjacent observed values.

After all intermittent missing scores are imputed, any scheduled PI/PR scores missing because the subject dropped out of the study will be imputed as follows: If the subject drops out due to adverse event (AE), the PI score will be imputed using a baseline observation carried forward (BOCF) method; if the subject drops out for other reasons, the PI/PR score will be imputed using the last observation carried forward (LOCF) method. PI data with missing baseline PI score will be excluded from the analysis.

For responder endpoints, subjects that drop out will be considered as non-responders for all assessment time points after their date/time of drop out. Similarly, if a subject receives rescue medication, then the subject will be treated as a non-responder for all subsequent timepoints.

No imputation for other efficacy or safety will be performed.

8.2 Efficacy Endpoints

8.2.1 Pain Intensity Difference

Pain Intensity Difference (PID) will be calculated based on Pain Intensity (PI) scores. PI will be assessed pre-dose, immediately prior to any use of rescue, and at each post-dose timepoint (15, 30, and 45 minutes and 1, 1.5, 2, 3, 4, 5, 6, 7, and 8 hours after T0) during the study using

an 11-point NPRS where 0 equates to no pain and 10 equates to the worst pain imaginable pain.

PID will be calculated at each time point i as $PID_i = PI_i - PIBL$ (Pain intensity score at time i and Pain intensity score at Baseline). All imputation, as described in Section 8.1.1, will be performed prior to the PID calculations.

PID_i will be summarized descriptively with sample size, mean, standard deviation, median, minimum, and maximum for each treatment group. The unadjusted *p*-value from a 1-sample t-test will be presented for each post-baseline nominal timepoint. Additionally, unadjusted p-values will be shown at each post-baseline nominal timepoint comparing the mean change from baseline values for each treatment, and of all DFN-15 treatments combined, to placebo. This will be done using an ANCOVA model with treatment as the main effect and both baseline pain intensity and BMI as covariates. To supplement this analysis, group mean of pain intensity over time will be displayed graphically at the nominal timepoints. These scores will also be presented in listings.

8.2.2 Summed Pain Intensity Difference

The primary efficacy endpoint is the summed pain intensity difference over the first 6 hours (SPID₆) between each of the DFN-15 dose levels and placebo. SPID₆ is created by summing the time weighted pain intensity differences (PID) scores using the area under the PID curve methodology.

All SPID calculations will be done using the standard trapezoidal rule:

SPIDx =

$$\sum_{i=0}^{x} \left(\frac{PID_i + PID_{i+1}}{2} \right) * (T_{i+1} - T_i)$$

Where: $PID_i = P_i - PIBL$ (Pain Intensity score at time i and Pain Intensity score at Baseline), $(T_{i+1} - T_i)$ is the Time difference in minutes between time i and time i+1, and $(T_{i+1} - T_i)$ is the Time difference in minutes between time i and time i+1.

Baseline PI will be defined as the last PI recorded prior to first dose. Time points will be selected for inclusion into specific SPID periods based on nominal time points (e.g., all scheduled assessments from Baseline to the Hour 6 assessment will be included in SPID₆).

Except for baseline, the actual date/times of assessments will be used in the SPID calculation whenever collected. For baseline, rather than the actual time recorded, baseline pain will be considered to be recorded at time 0(i.e., time of first dose).

All imputation, as described in Section 8.1.1, will be performed prior to the SPID calculations.

The individual SPID variables will also be presented in subject listings.

The secondary efficacy SPID outcomes (SPID₂, SPID₄, and SPID₈) are calculated similarly to SPID6 adjusting for the respective time periods.

All SPID endpoints will be analyzed using an ANCOVA with treatment as the main effect and both baseline pain intensity and BMI as covariates. Mean SPID values over time will be displayed graphically.

The results of the ANCOVA will be presented in summary tables with standard summary statistics as well as least square (LS) means, active dose level vs. placebo LS mean differences

(treated group – placebo), standard errors, confidence intervals (CI) and paired-comparison p-values with Dunnett's test.

8.2.3 Proportion of Responders

NPRS responders are defined as subjects who achieve \geq 30% (called 30% Responders) or \geq 50% (called 50% Responders) improvement in PI NPRS over the baseline value recorded at T0 at any time prior to first use rescue and up to 8 hours. All imputation as described in Section 8.1.1 will be performed prior to percent improvement and responder calculations. If any scheduled post-baseline NPRS score prior to rescue medication (if rescue was taken) meets or exceeds the threshold, regardless of if the subject subsequently loses their response, then the subject will be counted as an overall responder. Otherwise, the subject will be considered a non-responder. In addition, the proportion of subjects who achieve a 30%/50% improvement from baseline will also be calculated at each time point and displayed graphically.

Percent improvement = (baseline value - post-baseline value) × 100 / (baseline value)

The proportion of subjects experiencing \geq 30% and \geq 50% improvement in NPRS (responders) will be analyzed using chi square (CMH) test or, alternatively, a Fishers exact test if there are less than 5 subjects in any category. The testing of each dose level of DFN-15 vs. placebo will be performed separately.

Summary tables will present the by-treatment group descriptive statistics of proportions with active vs. placebo odds ratios, 95% confidence intervals and CMH chi-square or Fisher exact p-values. A cumulative proportion of responders figure will also be presented.

8.2.4 Pain Relief

Pain relief scores are captured on the 5-point pain relief scale (0= no pain relief, 1= little pain relief, 2= some pain relief, 3= a lot of pain relief, and 4= complete pain relief) at 15, 30, and 45 minutes and 1, 1.5, 2, 3, 4, 5, 6, 7, and 8 hours as well as immediately prior to any rescue use. Pain relief at each postdose timepoint will be summarized descriptively for each treatment group. All imputation, as described in Section 8.1.1, will be performed prior to presentation.

PR will be summarized descriptively with sample size, mean, standard deviation, median, minimum, and maximum for each treatment group. The unadjusted *p*-value from a 1-sample t-test will be presented for each post-baseline nominal timepoint. To supplement this analysis, group mean of pain relief over time will be displayed graphically at the nominal timepoints. Pain relief scores will also be presented in listings.

8.2.5 Total Pain Relief (TOTPAR)

Total Pain Relief (TOTPAR) over 2, 4, 6, and 8 hours. Total pain relief is calculated similarly to SPID replacing the PID values with the pain relief (PR) scores on the 5-point scale where 0= no pain relief, 1= little pain relief, 2= some pain relief, 3= a lot of pain relief, and 4= complete pain relief. All imputation, as described in Section 8.1.1, will be performed prior to the TOTPAR calculations.

All TOTPAR endpoints will be analyzed using an ANCOVA with treatment as the main effect and baseline pain intensity and BMI as covariates. The results of the ANCOVA will be presented in summary tables with standard summary statistics as well as least square (LS) means, active dose level vs. placebo LS mean differences (treated group – placebo), standard errors, confidence intervals and paired-comparison *p*-values with Dunnett's test. Mean TOTPAR values over time will also be displayed graphically.

8.2.6 Peak Pain Relief

Peak pain relief is defined as the maximum post-dose score (after imputation) that a subject reaches on the 5-point pain relief scale prior to any use of rescue medication (if rescue was taken). This will be summarized with standard summary statistics (count, mean, standard deviation, median, minimum, and maximum by treatment group.

Statistical Analysis Plan Version: 2.0

Effective Date: 08OCT2018

8.2.7 Time to Peak Pain Relief

Time to peak pain relief is defined as the earliest post-dose time that a subject reaches their maximum positive score on the 5-point pain relief scale prior to rescue medication (if rescue was taken). Subjects who do not record at least one positive pain relief score prior to use of rescue will be censored at 8 hours. Time to peak pain relief will be analyzed using Kaplan-Meier curves for each dose level of DFN-15 to placebo with the log-rank test. Estimated percentiles for time to peak pain relief will be tabulated by treatment group along with the number and percent of subjects censored. Additionally, a Kaplan-Meier curve will present cumulative percentages over time graphically.

8.2.8 Proportion of Subjects Satisfied with Treatment

The proportion satisfied with treatment is defined as ratio of subjects reporting treatment satisfaction scores of at least 2 on the 5-point scale (0= poor, 1= fair, 2= good, 3= very good, and 4= excellent) out of all mITT subjects. Summary tables will present the by-treatment group descriptive statistics of proportions for each active dose level vs. placebo, odds ratios, 95% confidence intervals and chi-square or Fisher exact *p*-values if chi-square test assumptions are not met. Treatment satisfaction scores will also be presented in listings. A summary of subject satisfaction scores as a continuous variable and ANCOVA analysis with treatment as the main effect and both baseline pain intensity and BMI as covariates will also be presented.

8.2.9 Time to Perceptible and Meaningful Pain Relief

Times to perceptible and meaningful pain relief will be measured using the double stopwatch method. For each randomized participant, two stopwatches will be started immediately after administration of study drug (T0). The first stopwatch will be given to the participant with the instructions to stop the watch at first perceptible pain relief (if they notice any decrease in the pain they have now). If the first watch is stopped, the second stopwatch will be given to the participant with the instructions to stop the watch if they have meaningful pain relief (pain relief that is meaningful to them). Perceptible pain relief will be summarized only for subjects that achieve meaningful pain relief (Confirmed Perceptible pain relief).

Subjects receiving rescue medication prior to stopping the stopwatch or who do not reach perceptible pain relief within 8 hours will be censored at 8 hours. Subjects will be similarly censored in calculations of meaningful pain relief.

Both time to perceptible and meaningful pain relief will be analyzed using Kaplan-Meier curves for each dose level of DFN-15 to placebo with the log-rank test. Estimated percentiles for time to perceptible/meaningful pain relief will be tabulated by treatment group along with the number and percent of subjects censored.

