At screening and upon admission/Check-in (Day 1) to the clinic, prior to dental surgery, subjects will be screened for alcohol consumption and illicit drug use by alcohol breathalyzer test and urine drug screen, respectively. Subjects continuing to meet I/E criteria will proceed to undergo their planned surgery for extraction of the impacted mandibular molars on both sides. As a prerequisite for randomization, subjects will be required to report within 6 h post-surgery (Baseline period): a) "moderate" to "severe" baseline pain as characterized on a 4-point categorical pain intensity (PI) scale (0= none, 1= mild, 2=moderate, 3= severe), and b) a score of ≥5, on the 11-point Numerical Pain Rating Scale (NPRS) where 0 represents 'no pain' and 10 represents 'worst pain imaginable', on the provided paper diary. Eligible subjects will be randomized and will receive a single dose of the assigned study treatment (a total volume of 10 mL). The start time of dosing will be recorded as T0. Subjects will be randomized and administered the study medication within 15 minutes of meeting the post-operative inclusion criteria (baseline score).

Subjects with inadequately controlled pain symptoms may request rescue analgesic medication. The rescue medication for this study will be 1-2 oxycodone 5 mg/acetaminophen 325 mg q 4 h PRN. Subjects will be encouraged to delay using the rescue medication if their pain is tolerable until 120 minutes post-dose of study medication. A subject who is administered rescue pain medication will continue completing pain assessments until 8 hours after treatment initiation. The use of ice packs will not be allowed in the 8-hour observation period. All randomized subjects will be provided with a paper diary to record pain assessments. A subject training program will be implemented to ensure that all subjects understand the relevant scales and assessments prior to study participation. At study medication administration, two stopwatches will be started, to measure times to 'perceptible' and 'meaningful' pain-relief. Subjects will be instructed to stop the first stopwatch when they first perceive pain relief to occur (time to perceptible relief). Subjects will be instructed to stop the second stopwatch when they first experience meaningful pain relief (time to meaningful relief). Stopwatch times of perceptible relief and meaningful relief will be recorded using exact stopwatch time displayed.

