8.3 General Analysis Methods

SPID and TOPAR endpoints will use Dunnett's test to account for multiplicity within each of those endpoints. All other *p*-values are presented without adjustment for multiplicity. The mITT population will be primary population used for all efficacy analyses. The PP population will be used as a supplemental analysis for SPID, TOTPAR, PID by timepoint, PR by timepoint, and peak pain relief.

In all cases, the null hypothesis being tested is that the means of the two treatment groups are equal, and the alternative is that the means are not equal:

- H₀: there is no treatment difference
- H_A: there is a treatment difference

If more than 1 center is used, then center effect will be added to the SPID6 ANCOVA model to investigate the impact. If the center effect is significant at the 0.05 level, then center will be added to the log-rank test for time to meaningful and perceptible pain relief analyses. Additionally, treatment-center interactions will be tested in the ANCOVA analysis of the SPID6 endpoint. If this interaction is significant at the 0.10 level, then the interaction term will be included in a sensitivity analysis.

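### SAP 8.2.9 limits perceptible relief to subjects who reach meaningful relief, against its own censoring rule and mITT population, and gives first-watch-only subjects no stated status

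*SAP*

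**What the plan says.** SAP 8.2.9 describes the two-stopwatch method, with the watches in sequence: "If the first watch is stopped, the second stopwatch will be given to the participant". On perceptible relief it then says: "Perceptible pain relief will be summarized only for subjects that achieve meaningful pain relief (Confirmed Perceptible pain relief".

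The next paragraph sets the censoring. It covers "Subjects receiving rescue medication prior to stopping the stopwatch" and those "who do not reach perceptible pain relief within 8 hours will be censored at 8 hours", and it applies the same censoring to meaningful relief. Both endpoints get Kaplan-Meier curves and a log-rank test of each dose against placebo, with percentiles "tabulated by treatment group along with the number and percent of subjects censored".

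On population, SAP 8.3 says: "The mITT population will be primary population used for all efficacy analyses". The mITT definition in SAP 4.1 asks for randomisation, dosing and one post-dose pain intensity score, and has no condition on relief. Table 14.2.9 and Figure 14.2.6 are both labelled mITT. The figure title contains the word *Confirmed*; the table title does not.

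The protocol (6.3.7 and 8.5.3) defines the endpoint by the first watch alone and censors every subject without the event at the last evaluation. It also lets the SAP prevail where the two differ (8.3.1).

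**The concern.** Reaching meaningful relief happens after randomisation and may depend on treatment. A comparison restricted to those who reach it is no longer a comparison of the randomised arms. It asks how fast relief was first noticed among subjects who all went on to good relief, and discards the difference in how many got there.

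The sentence also does not fit the rules around it, so two programmers could build different datasets from the same section. Faster onset is a stated expectation for DFN-15 (protocol section 1), and time to perceptible relief is a listed key secondary endpoint (protocol 8.2.1). If the wording stays open, the reading could be settled after the treatment codes are known.

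**Working it through.** The plan gives no power, event count or relief rate for this endpoint, so there is no figure to reproduce. The main check traces each stopwatch outcome through the text.

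| Outcome | Literal restriction | 8 h censoring paragraph |
|---|---|---|
| Both watches stopped within 8 h, before rescue | Included, event | Event |
| First watch never stopped | Left out | Censored at 8 h |
| First watch stopped, second never stopped | Left out | Not clearly covered: perceptible relief was reached |
| First watch stopped, then rescue, then second watch stopped | Left out, because the same censoring applies to meaningful relief | Not clearly covered, as in the row above |

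Row 2 is the contradiction. With sequential hand-over, a subject who never perceives relief cannot be in the restricted set, yet the next paragraph censors that subject. The planned percent censored would be zero or close to it under the restriction. Rows 3 and 4 are the gap: no sentence says event, censored or excluded.

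**Illustration.** Inputs from the documents: 120/4 = 30 per arm (SAP 2.5, 2.6) and two-sided 0.05 (SAP 3.0). All else is assumed: lognormal onset, median 0.5 h unless stated, log-SD 0.6; no watch stopped after rescue; the first-watch-only group is 25/50/75% of unconfirmed subjects in both arms. There were 10,000 simulated trials per setting (Monte Carlo SE at most √(0.25/10,000) = 0.5 points). Log-rank power, active vs placebo:

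| Scenario | All unconfirmed censored at 8 h | First-watch-only excluded | First-watch-only counted as events | Literal subset |
|---|---|---|---|---|
| 1: confirmed 70% vs 30%, equal onset | 88% | 81/68/42% | 65/38/16% | 6–7% |
| 2: 70% vs 30%, onset 0.5 vs 0.75 h | 93–94% | 91/84/69% | 84/72/63% | 30–31% |
| 3: 70% vs 40%, onset 0.5 vs 0.6 h | 70–71% | 64/53/37% | 55/40/29% | 11–12% |

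Scenario 1 at the 50% share shows where the spread comes from. Confirmed subjects: 0.70 × 30 = 21 active, 0.30 × 30 = 9 placebo. First-watch-only: 0.5 × 9 = 4.5 and 0.5 × 21 = 10.5. Relief at 8 h, active vs placebo:
- censored: 21/30 = 70% vs 9/30 = 30%
- excluded: 21/25.5 = 82% vs 9/19.5 = 46%
- counted as events: 25.5/30 = 85% vs 19.5/30 = 65%
- literal subset: 21/21 = 100% vs 9/9 = 100%

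Exclusion can also create a difference. With confirmed relief 50% in both arms and first-watch-only shares of 25% active and 50% placebo, exclusion rejects in 10.5% of trials, against 5.0% when those subjects are censored. That is a null for confirmed relief only. Any perceptible relief truly differs there (0.50 + 0.25 × 0.50 = 62.5% vs 0.50 + 0.50 × 0.50 = 75%), and a test of it rejects in 17%.

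A second set of assumptions (exponential onset, 2,000 trials per setting, four settings with a drug effect) gave 76–90% censored, 59–88% excluded, 42–72% as events and 6–20% in the literal subset. With no difference between arms, all four readings rejected in 5–7%.

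**The case against.** The best defence is that the intent can be worked out. *Confirmed*, the 8 h rule, the planned count of censored subjects, the mITT rule and the mITT Kaplan-Meier figure all fit one reading: the event is the first-watch time if the second watch is also stopped, analysed in all mITT subjects. The restricting sentence also concerns what is summarised, while the log-rank sentence carries no restriction. Much of this stands, and a reader should not infer that the sponsor plainly means to test a selected subset. But the one sentence on who is included says the opposite, and even the favourable reading leaves the first-watch-only subject to be guessed.

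A reader might also infer that relief obtained after rescue could confirm an earlier first-watch time, since SAP 2.2 says: "A subject who is administered rescue pain medication will continue completing pain assessments until 8 hours after treatment initiation". The documents do not support that. SAP 8.2.9 censors for meaningful relief in the same way, so a subject rescued before stopping the second watch has not reached it for analysis. Protocol 3.1 also disregards post-rescue assessments. SAP 8.1.1 changes that for pain intensity and relief scores, not for the stopwatches.

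A third inference is that adding confirmation breaches the protocol. It does not, because the protocol lets the SAP prevail.

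Two smaller points are fair. Protocol Appendix A (note o) provides both watches at dosing, so sequential hand-over rests on SAP 8.2.9 and protocol 6.3.7. And the rescue half of the censoring rule need not conflict with the restriction; the conflict lies in the half about never perceiving relief.

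**Conclusion.** The concern holds as a contradiction within SAP 8.2.9, a conflict with the mITT population, and an unstated status for subjects who stop only the first watch. Followed as written, the restriction would give a comparison that is not of the randomised arms. The surrounding cues point to a sound intention, which makes the correction easy but does not replace it.

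The reach is small. This is one secondary endpoint whose p-values "are presented without adjustment for multiplicity". SPID6 and time to meaningful relief are not affected, and Listing 16.2.10.3 would let any reading be recomputed.

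It would be tempting to read the fall from 88% to about 7% as power lost. The documents do not support that: every relief rate and onset time is assumed, relief after rescue is not modelled, and the columns test different endpoints. The simulations show only that the readings can give different answers. It should be fixed before unblinding.

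**What to change.** Replace the restricting sentence in SAP 8.2.9 with: *Time to confirmed perceptible relief is analysed in all mITT subjects; the event is the first-watch time if the second watch is also stopped within 8 h and before rescue; all other subjects are censored at 8 h.* The rescue clause only makes explicit what the section already implies, and 8 h keeps the SAP's own censoring time. Give Table 14.2.9 and Figure 14.2.6 matching titles. Settle both before unblinding.

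Reporting time to any perceptible relief (the protocol's first-watch endpoint) beside it in all mITT subjects is an optional sensitivity analysis. Its downside is one more unadjusted test.

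The cost is one replaced sentence, a censoring flag and a corrected title, plus a further table and figure if the optional analysis is taken up. No new data are needed.
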